### 8.2.3. Electrocardiograms

- A single 12-lead electrocardiogram (ECG) will be obtained as outlined in the SoA (see Section 1.3) using an ECG machine that automatically calculates the heart rate and measures PR, QRS, QT, and QTc intervals.
- Participants must be supine for approximately 5 to 10 minutes before ECG collection and remain supine but awake during ECG collection.
- The Investigator or qualified designee will be responsible for reviewing the ECG to assess whether the ECG is within normal limits and to determine the clinical significance of the results. These assessments will be recorded in the source documents and the eCRF.

### 8.2.4. Clinical Safety Laboratory Assessments

• Detailed instructions on the procedure for collection, processing, storage, and shipment of the samples for laboratory analyses will be provided in the Laboratory Study Manual. All sample analyses will be performed by Alexion or its designee.

- See Section 10.2 for the clinical laboratory tests to be performed and the SoA (Section 1.3) for their timing and frequency.
- If a suspected event of BTH occurs, LDH, PK, and PD samples will be collected and analyzed. If the suspected event of BTH does not occur at a scheduled visit, an unscheduled visit should be conducted for evaluation of the participant and collection of the required LDH, PK, and PD samples.
- The Investigator must review the laboratory report, document this review, and record any clinically relevant changes occurring during the study in the AE section of the eCRF. The laboratory reports must be filed with the source documents. Clinically significant abnormal laboratory findings are those which are not associated with the underlying disease, unless judged by the Investigator to be more severe than expected for the participant's condition.
- All laboratory tests with values considered clinically significantly abnormal during participation in the study should be discussed by the Investigator and Medical Monitor.
  - If such values do not return to normal/baseline within a period of time judged reasonable by the Investigator, the etiology should be identified, and Alexion notified.
  - All protocol-required laboratory assessments, as defined in Section 10.2, must be conducted in accordance with the laboratory manual and the SoA.
  - If laboratory values from non-protocol specified laboratory assessments performed at the institution's local laboratory require a change in participant management or are considered clinically significant by the Investigator (eg, SAE or AE or dose modification), then the results must be recorded in the CRF.

# 8.3. Adverse Events and Serious Adverse Events

The definitions of AEs and SAEs are specified in Section 10.3.

AEs will be reported to the Investigator or qualified designee by the participant (or when appropriate, by a caregiver, surrogate, or the participant's legally authorized representative).

The Investigator and any qualified designees are responsible for detecting, documenting, and recording events that meet the definition of an AE or SAE and remain responsible for following up of AEs that are serious, considered related to the study drug or study procedures, or that caused the participant to discontinue the study drug (see Section 7).

Definitions and procedures for recording, evaluating, follow-up, and reporting AEs and SAEs are outlined in Section 10.3 (Appendix 3).

# 8.3.1. Time Period and Frequency for Collecting Adverse Event and Serious Adverse Event Information

All AEs will be collected from the signing of the Informed Consent Form until the follow-up call.

All SAEs will be recorded and reported to Alexion or designee within 24 hours of awareness, as indicated in Section 10.3. The Investigator will submit any updated SAE data to Alexion within 24 hours of it being available.

Investigators are not obligated to actively seek AEs or SAEs after conclusion of the study participation. However, if the Investigator learns of any SAE, including a death, at any time after a participant has exited the study, and he/she considers the event to be reasonably related to the study drug, the Investigator must promptly notify Alexion.

## 8.3.2. Method of Detecting AEs and SAEs

The method of recording, evaluating, and assessing causality of AE and SAE and the procedures for completing and transmitting SAE reports are provided in Section 10.3.

Care will be taken not to introduce bias when detecting AEs and/or SAEs. Open-ended and non-leading verbal questioning of the participant is the preferred method to inquire about AE occurrences.

## 8.3.3. Follow-up of AEs and SAEs

After the initial AE/SAE report, the Investigator is required to proactively follow each participant at subsequent visits/contacts. All SAEs and AEs of special interest (AESI) (as defined in Section 8.3.6), will be followed until resolution, stabilization, the event is otherwise explained, or the participant is lost to follow-up (as defined in Section 7.3). Further information on follow-up procedures is provided in Section 10.3.

### 8.3.4. Regulatory Reporting Requirements for SAEs

- Prompt notification by the Investigator to Alexion of a SAE is essential so that legal obligations and ethical responsibilities towards the safety of participants and the safety of a study drug under clinical investigation are met.
- Alexion has a legal responsibility to notify both the local regulatory authority and other regulatory agencies about the safety of a study drug under clinical investigation. Alexion will comply with country-specific regulatory requirements relating to safety reporting to the regulatory authority, Institutional Review Board (IRB)/Independent Ethics Committee (IEC), and investigators.
- Investigator safety reports must be prepared for suspected unexpected serious adverse reactions (SUSARs) according to local regulatory requirements and sponsor policy and forwarded to Investigators as necessary.
- An Investigator who receives an investigator safety report describing a SAE or other specific safety information (eg, summary or listing of SAEs) from Alexion will review, sign a document stating they have reviewed it, and then file it along with the IB and will notify the IRB/IEC, if appropriate according to local requirements.

### 8.3.5. Pregnancy

Pregnancy testing must be performed on all WOCBP at protocol-specified timepoints in the SoA (Section 1.3). Serum samples will be collected at Day 85, Day 1, and Day 351/ET. At all other

time points urine samples will be collected for pregnancy test. Pregnancy tests (urine or serum) may also be performed at any time during the study at the Investigator's discretion.

A negative pregnancy test is required for WOCBP before study drug administration.

- Details of all pregnancies in female participants and, if indicated, female partners of male participants will be collected after the start of study drug and until the termination of the pregnancy.
- If a pregnancy is reported, the Investigator should inform Alexion within 24 hours of learning of the pregnancy and should follow the procedures outlined in Section 10.4.
- Abnormal pregnancy outcomes (eg, spontaneous abortion, fetal death, stillbirth, congenital anomalies, ectopic pregnancy) are considered SAEs. Pregnancy alone is not considered an AE.

If a participant becomes pregnant, the study drug must be immediately discontinued, and Alexion must be notified as per Section 10.4. Each pregnancy will be followed to term and Alexion notified regarding the outcome.

## 8.3.6. Adverse Events of Special Interest

Meningococcal infections will be collected as AESI.

## 8.4. Treatment of Overdose

For this study, any dose of study drug greater than that specified in the label will be considered an overdose.

Accidental overdose without any association with laboratory abnormalities or clinical symptoms should not be considered as an AE. Overdose must be reported by the Investigator within 24 hours to Alexion regardless of its association with or without an AE.

Alexion does not recommend specific treatment for an overdose.

In the event of an overdose, the Investigator should:

- 1. Contact the Medical Monitor immediately.
- 2. Closely monitor the participant for any AE/SAE.
- 3. Obtain a serum sample for PK analysis if requested by the Medical Monitor (determined on a case-by-case basis).
- 4. Document the quantity of the excess dose as well as the timing of the overdose in the eCRF.

Decisions regarding dose interruptions will be made by the Investigator in consultation with the Medical Monitor based on the clinical evaluation of the participant.

# 8.5. Pharmacokinetics/Pharmacodynamics Sampling

### 8.5.1. Sample Collection During the Screening Period

Serum samples will be collected for free and total C5 analyses (before eculizumab dosing) during Screening on Day -57 and Day -29. The predose (within 0.5 hours prior to the start of infusion) free C5 sample may be drawn through the venous access created for the dose infusion, prior to administration of the dose. All collection times will be recorded in the eCRF. In the event of BTH, a serum sample for PK/PD analysis will be collected.

In the event of an unscheduled visit, PK and PD blood sample will be collected as soon as possible.

## 8.5.2. Sample Collection during Confirmation Visit Through Follow-up

Blood samples for determination of serum drug concentrations and PD assessments will be collected before and after administration of study drug at the time points as specified in the SoA (Section 1.3). The predose (within 0.5 hours prior to the start of infusion) PK/PD sample may be drawn through the venous access created for the dose infusion, prior to administration of the dose. End-of-infusion (within 0.5 hours after the end of infusion) PK/PD samples will be drawn from the participant's opposite, non-infused arm. All collection times will be recorded in the eCRF. In the event of BTH, a serum PK/PD sample will be collected.

## 8.6. Pharmacodynamics

Changes in serum free C5 and total C5 concentrations over time will be assessed.

# 8.7. Genetics

No samples will be collected for genetic analyses.

# 8.8. Biomarkers

Biomarkers will not be evaluated in this study.

# 8.9. Immunogenicity Assessments

Antibodies to ravulizumab will be evaluated in serum samples collected predose (within 5 to 90 minutes prior to the start of infusion of study drug) from all participants according to the SoA (Section 1.3).

Additionally, serum samples will be collected at the final visit from participants who discontinue study drug or are withdrawn from the study.

In the event of a BTH, serum samples for ADA analysis will be collected per SoA (Table 1).

Serum samples will be screened for antibodies binding to ravulizumab and the titer of confirmed positive samples will be reported. Other analyses may be performed to verify the stability of antibodies to ravulizumab and/or further characterize the immunogenicity of ravulizumab.

The detection and characterization of antibodies to ravulizumab will be performed using a validated assay method by or under the supervision of Alexion. Samples may be further

characterized to determine the titer and the presence of neutralizing antibodies if deemed necessary. Samples may be stored for a maximum duration according to local regulations following the last participant's last study visit at a facility selected by Alexion.

# 8.10. Patient-Reported Symptoms and Health Resource Utilization questionnaires

Patient-reported PNH symptoms (PRS) and Health Resource Utilization (HRU) data, will be collected at Day 1 (baseline), Day 183 and Day 351/ET in the eCRF by the Investigator and study-site personnel for all participants throughout the study. Protocol-mandated procedures, tests, and encounters are excluded.

For PRS, each participant will record the presence or absence of the signs and symptoms of PNH: fatigue, chest pain, abdominal pain, dyspnea, dysphagia, headache, confusion, erectile dysfunction (if applicable), discoloration of urine, discoloration of eyes (see Appendix 10.5.1).

For HRU, the Investigator or designee will record for each participant the number of clinic visits, emergency services utilized, hospitalization, missed work and also record the number of times the participant had darkened urine (see Appendix 10.5.2).

# 8.11. Visits during COVID-19 Pandemic

To ensure patient safety and treatment continuity during the COVID-19 pandemic, the following will apply until patients are able to resume study visits at the site.

Patients may have an opportunity to receive ravulizumab administration (see Section 1.3 for SoA) remotely at a medical facility that is located near the patient's home or at the patient's home with the permission of the Investigator in accordance with all national, state, and local laws or regulations of the pertinent regulatory authorities.

Remote visit options may be at the Investigator's discretion and oversight, in accordance with the local regulations, and conducted by a qualified healthcare personnel. Information about AEs concomitant medications, samples for protocol-defined laboratory parameters must be sent to the Investigator's site for evaluation on the day of the remote visit.

# 9. STATISTICAL CONSIDERATIONS

# 9.1. Statistical Hypotheses

This is an estimation study; no formal statistical hypotheses will be tested.

# 9.2. Sample Size Determination

The proposed sample size for this estimation study is approximately 20 participants. The range of possible proportions of participants experiencing free C5-associated BTH during the Treatment Period (with 95% exact confidence intervals) is as follows:

Proportion of BTH (participants with BTH/total population)	95% CI
95% (19/20)	75%, 100%
75% (15/20)	51%, 91%
50% (10/20)	27%, 73%
25% (5/20)	9%, 49%
10% (2/20)	1%, 32%
5% (1/20)	0%, 25%
0% (0/20)	0%, 17%

# 9.3. **Populations for Analyses**

Efficacy analyses will be performed on the Full Analysis Set (FAS). The FAS is the primary population for all efficacy analyses. The FAS will include all participants who receive at least 1 dose of ravulizumab.

Safety analyses will be performed on the Safety Set, defined as all participants who receive at least 1 dose of ravulizumab.

Pharmacokinetic analyses will be performed on the PK analysis set, defined as all participants who receive at least 1 dose of study drug and who have evaluable PK data.

# 9.4. Statistical Analyses

Details of the statistical analyses described below will be specified in a separate Statistical Analysis Plan (SAP) before first database lock and analysis, including procedures for accounting for missing data. Any change to the data analysis methods described in the protocol will require an amendment only if it changes the primary or secondary objectives or the study conduct. Any other change to the data analysis methods described in the protocol or SAP, and the justification for making the change, will be described in the clinical study report (CSR). Additional analyses of the data to address the impact of COVID-19 may be conducted as deemed appropriate.

All data collected will be presented using summary tables, figures, and data listings. All data, as well as any outcomes derived from the data, will be presented in detailed data listings. Graphical displays may also be provided, when appropriate. All analyses will be performed using SAS® release, version 9.4 or higher (SAS Institute Inc., Cary, NC, USA) or other validated statistical software. Continuous variables will be summarized using descriptive statistics, including the number of observations, and mean, standard deviation, median, minimum, and maximum values.

Categorical variables will be summarized by frequency counts and the percentage of participants. All statistical tests performed will be based on a 2-sided 5% level of significance unless otherwise specified.

A CSR to summarize efficacy, safety, PK, PD, and immunogenicity data will be produced at study completion.

# 9.4.1. Efficacy Analyses

The primary efficacy endpoint is proportion of participants who experience free C5-associated BTH. The proportion along with a two-sided 95% exact CI will be calculated. The same approach will be employed for proportion of participants who experience BTH and stabilized hemoglobin.

The percentage change in LDH will be analyzed using a mixed model for repeated measures (MMRM) (Mallinckrodt, 2001; Mallinckrodt, 2004) with the fixed categorical effects of study visit, and the continuous fixed covariate of baseline LDH. Baseline is defined as the average of all assessments analyzed by the central laboratory prior to first study drug administration. The Kenward-Roger approximation will be used to estimate denominator degrees of freedom. A p-value testing whether percent changes differ from zero at each visit will be calculated.

Transfusion rates will be summarized.

Exploratory data of PRS and HRU will be summarized descriptively.

## 9.4.2. Safety Analyses

All safety data will be summarized using the Safety Set.

## 9.4.2.1. Analysis of Adverse Events

The analysis and reporting of AEs will be based on treatment-emergent adverse events (TEAEs), defined as AEs with onset on or after the first dose of ravulizumab. The incidence of TEAEs will be summarized by system organ class (SOC) and preferred term (PT), with additional summaries showing severity, relationship to study drug, TEAEs leading to study drug discontinuation, and TEAEs resulting in death. Summaries of treatment-emergent serious adverse events (TESAEs) will also be summarized by SOC and PT, with an additional summary showing relationship to study drug. All AEs will be coded using the latest MedDRA version.

# 9.4.2.2. Analysis of Clinical Laboratory Parameters, Vital Sign Measurements and Electrocardiogram Parameters

Laboratory measurements as well as their changes from baseline at each visit and shift from baseline, if applicable, will be summarized. Data on ECGs, including ECG interpretation heart rate, PR, QRS, QT, and QTc intervals, and vital signs will also be summarized.

## 9.4.3. Demographics and Baseline Characteristics

Participant demographic and baseline characteristics will be summarized by treatment group, using the Safety Set. Summary statistics will be presented. No formal hypothesis testing will be performed.

## 9.4.4. Participant Disposition

The number of participants screened, treated, completing the study, discontinued from the study, reasons for discontinuation, and those included in each analysis set will be summarized.

Important protocol deviations will be summarized by prespecified deviation categories.

## 9.4.5. Prior and Concomitant Medications

Any medication taken up to 28 days prior to the start of Screening or are ongoing at the first dose of study drug will be considered prior medications or concomitant medications. Prior and concomitant medications will be summarized for all participants in the Safety Analysis Set, including immunosuppressant therapies for relapse prevention and acute relapse treatment. Medications will be coded using the World Health Organization Drug Dictionary based on the most current version available at the time of the analyses.

## 9.4.6. Pharmacokinetics and Pharmacodynamics Analyses

Individual serum concentration data for all participants who receive at least 1 dose of ravulizumab and who have evaluable PK data will be used to derive PK parameters for ravulizumab.

Graphs of mean serum concentration-time profiles will be constructed. Graphs of serum concentration-time profiles for individual participants may also be provided. Actual dose administration and sampling times will be used for all calculations. Descriptive statistics will be calculated for serum concentration data at each sampling time, as appropriate. Assessment of population-PK may be considered using data from this study or in combination with data from other studies.

Pharmacodynamic analyses will be performed for all participants who receive at least 1 dose of ravulizumab and who have evaluable PD data.

Descriptive statistics will be presented for all ravulizumab PD endpoints at each sampling time (Section 1.3). The PD effects of ravulizumab administered IV will be evaluated by assessing the absolute values and changes and percentage changes from baseline in total and free C5 serum concentrations over time, as appropriate.

Immunogenicity analyses and subgroup and sensitivity analyses will be described in the SAP and finalized before database lock.

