6.4. Visit Windows

Study visits will be defined through the use of windows based on the list of visits described in Section 1.3 of the Protocol. For all assessments, the number of days from baseline will be calculated using the following formula: (date of assessment) - (date of first study treatment) + 1. This number of days will be used to assign analysis visits. This may not always correspond to the eCRF visit.

All post-baseline records including those that occurred outside the specified protocol windows will be assigned to an appropriate analysis visit by using the following scheme and will be included in the analysis of the specific assessment, where applicable.

Generally, the lower bound for each analysis visit window is defined as the midpoint of the target dates between 2 consecutive scheduled visits. The upper bound of the last visit window is set as the target date + 7 days. If the date of assessment falls between the lower and the upper bound for a visit as defined in the schedule of assessments (see Section 1.3 of the protocol), then it will be assigned to that visit. If the interval separating 2 scheduled visits is an even number of days, that middle day will be included in the lower bound of the next visit window.

If only 1 record is within an analysis visit window, the data from that record will be used in the analysis. If more than 1 record is within the same analysis visit window, the record closest to the midpoint of the

This document is confidential.

SAP Version: 2.0 09-Feb-2023

Controlled Document ID: 3903A.02, Effective Date 31-Aug-2020

interval will be used in the analysis. If 2 records are "tied" before and after the middle of the interval, the earlier record will be used in the analysis. Participants who switch to q6w dosing will likely have more than 1 record in some visit windows. The decision rules described above will be applied to the q6w visits to determine which measurements will be used in the analysis.

See Table 2 for visit window definitions.

Table 2: Visit Windows (Days)

Visit	Nominal Day	Visit Window		
Screening Period				
Day -85	-85	-85 – -79		
Day -71	-71	-78 – -65		
Day -57	-57	-64 – -51		
Day -43	-43	-50 – -37		
Day -29	-29	-36 – -23		
Day -15	-15	-22 – -1		
Confirmation Visit				
Day 1	1	1 - 1		
Evaluation Period				
Day 15	15	8 – 42		
Day 71	71	43 – 98		
Day 127	127	99 – 154		
Day 183	183	155 – 210		
Day 239	239	211 – 266		
Day 295	295	267 – 322		
Day 351	351	323 – 378		
Follow-up	407	379 – max		

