9.2. Presentation of Concentration Data

9.2.1. Handling of Missing Data

Missing concentration data for all participants who are administered study treatment will be considered as non-informative missing and will not be imputed. No concentration estimates will be provided for missing sample values.

9.2.2. Handling of the Difference between the Scheduled (Nominal Time) and the Actual Sampling Times (Actual Time)

For all sampling times, the actual sampling times relative to dosing are calculated as the difference between the actual clock time of sampling and the actual clock time of dosing. The actual postdose sampling times relative to dosing expressed in hours and rounded off to 3 decimal digits are used. The predose sampling time will be reported as 0 (0.000), regardless of the time difference between the predose sampling and dosing. Scheduled sampling times are presented in concentration tables. If the actual time of sampling is missing, the nominal time is used.

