9.2.4. Summary of PK Concentrations

For PK concentration summary, the following rules apply:

- PK concentrations BLQ in predose samples and in samples taken before the time of the first quantifiable value are set to half the lower limit of quantification (0.5 ug/mL).
- The PK concentrations BLQ after quantifiable concentration are set to 0;
- The sampling time of predose samples relative to dosing will be treated as 0;
- Drug concentrations will be summarized by nominal timepoint;
- Descriptive statistics will be performed;
- No further imputation is applied to any missing values.

Ravulizumab concentrations will be summarized descriptively by visit and timepoint (in relevant concentration units) using descriptive statistics (n, number and percent of participants with BLQ, arithmetic mean, geometric mean, SD, arithmetic and geometric coefficient of variation (CV) %, minimum, median and maximum) presented according to the following reporting precision.

Variable	Summarized with:
Minimum, Maximum	3 significant digits or as needed based on actual measured values
Arithmetic Mean, Geometric Mean, Median	4 significant digits or as needed based on actual measured values
SD	5 significant digits or as needed based on actual measured values
CV%, and Geometric CV%	1 decimal place or as needed based on actual measured values

Mean (± SD) concentration-time profiles, on linear and log-linear scales versus nominal time will be generated.

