9.3. PK Parameters Derivation

Only C_{trough}, C_{max}, accumulation ratio, and attainment of steady state for ravulizumab will be reported. No other PK parameters are possible to calculate due to limited sampling schedule.

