9.3.1. PK Parameters Summarization

C_{max} and C_{trough} will be summarized descriptively using n, arithmetic mean, SD, CV%, minimum, median, maximum, geometric mean, and geometric CV%.

Accumulation ratio will be calculated for both C_{max} and C_{trough} following the first and last maintenance dose of ravulizumab.

This document is confidential

SAP Version: 2.0 09-Feb-2023

Controlled Document ID: 3903A.02, Effective Date 31-Aug-2020

Attainment of steady state will be calculated using the slope, corresponding 95% CI, and P-value of Ctrough values at Days 15, 71, 127, 183, 239, 295, and 351.

The model will be used to assess whether steady state was achieved for ravulizumab where sufficient data are available. Aggregate assessment of trough concentrations by repeated measures ANOVA will be used to evaluate attainment of steady state. The approach is based on the comparison of log-transformed trough concentration values to the mean of the results for all the succeeding doses up to Day 351.

Repeated measures analysis will be carried out on log-transformed trough levels (predose concentrations) for Days 15, 71, 127, 183, 239, 295, and 351.

The example SAS code will be:

PROC MIXED DATA=xx;

CLASS dose time patient id;

MODEL log(PK parameter) = treatment treatment*time / DDFM=KR;

REPEATED / TYPE=UN SUBJECT=patient_id(dose);

LSMEANS dose*time;

RUN;

The DDFM = KR (KenwardRoger) option performs the degrees-of-freedom calculations detailed by Kenward and Roger (1997). As recommended the denominator degrees of freedom for the fixed effects will be estimated as the most appropriate method in the mixed-model analysis.

Contrasts will be tested between a particular time point and the pooled mean over all remaining time points:

Day 15 / the average pre-dose Day 71 through Day 351

Day 71 / the average pre-dose Day 127 through Day 351

Day 127 / the average pre-dose Day 183 through Day 351

Day 183 / the average pre-dose Day 239 through Day 351

Day 239 / the average pre-dose Day 295 through Day 351

Day 239 / the average pre-dose Day 351

The first non-significant comparison will be concluded to be the day number (Day x) at which steady state concentrations are attained. The p-value for difference of Least Square Means (LSM), LSM Ratio, and the 95% confidence interval for the contrasts will be provided.

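### The SAP's trough and steady-state analysis groups samples by study day with no criterion for time since the previous infusion, although the protocol calls for actual times

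*Protocol*

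**What the plan says.** Protocol 9.4.6 sets the rule for PK timing: "Actual dose administration and sampling times will be used for all calculations". The same paragraph adds: "Descriptive statistics will be calculated for serum concentration data at each sampling time, as appropriate".

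SAP 9.2.2 keeps actual times for samples after a dose ("The actual postdose sampling times relative to dosing expressed in hours and rounded off to 3 decimal digits are used") and treats samples before a dose differently: "The predose sampling time will be reported as 0 (0.000), regardless of the time difference between the predose sampling and dosing". SAP 9.2.4 says "Drug concentrations will be summarized by nominal timepoint".

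SAP 9.3 limits the reported PK results to C_trough, C_max, accumulation ratio and attainment of steady state, because "No other PK parameters are possible to calculate due to limited sampling schedule". For steady state, SAP 9.3.1 says "Repeated measures analysis will be carried out on log-transformed trough levels (predose concentrations) for Days 15, 71, 127, 183, 239, 295, and 351". Its example code declares time as a class variable, and its contrasts are between labelled days. It gives no allowed range, exclusion or model term for time since the previous infusion.

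SAP 6.4 says "All post-baseline records including those that occurred outside the specified protocol windows will be assigned to an appropriate analysis visit". It also applies the same selection rules to q6w visits, so they fall into windows built for the q8w schedule.

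Protocol Table 2 schedules PK/PD samples on Days 1, 15, 71, 127, 183 and 351/ET and at unscheduled visits, but not on Days 239 or 295. It marks no infusion on Day 351. SAP 14 lists two changes from the protocol, the wording of the PK endpoint and the added Enrolled Set. PK time handling is not among them.

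**The concern.** A trough concentration is interpretable only with the time since the last infusion. Nothing in the SAP requires the samples labelled as one trough day to share that time, even approximately. Visit windows, q6w dosing, supplemental doses, early termination and event-triggered sampling all change it.

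At stake is the reading of exposure in patients who, according to Protocol 4.2, were excluded from the Phase 3 study in eculizumab-experienced participants. Differences in timing would appear as differences between visits or participants, and would carry into the trough slope and the day on which steady state is declared. The error need not be random: under Protocol 6.6.2, q6w dosing follows free C5-related breakthrough hemolysis, so off-interval samples would come largely from the participants whose exposure is of most interest.

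**Working it through.** The documents give no figure for trough timing. What can be reproduced is SAP Table 2, from the midpoint rule.

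**1. Analysis windows.** For Day 71, the lower bound is (15 + 71)/2 = 43. The next window starts at (71 + 127)/2 = 99, so Day 71 covers 43–98, as printed. The rule also returns the printed windows for Days 183 (155–210), 239 (211–266), 295 (267–322) and 351 (323–378).

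**2. Time since last infusion when every visit is in window.** Inputs are the windows in Protocol Tables 2 and 3: Day 1 none, Day 15 ±2 days, later visits ±7 days. Range = nominal interval ± (window of the dosing visit + window of the sampling visit).

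- Day 15: 14 ± (0 + 2) = 12–16 days
- Day 71: 56 ± (2 + 7) = 47–65 days
- Days 127 to 351, q8w: 56 ± (7 + 7) = 42–70 days
- q6w, between two visits that each have ±7 days: 42 ± (7 + 7) = 28–56 days

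**3. What can fill Days 239 and 295.** A compliant Day 183 sample falls on Days 176–190, inside 155–210. A compliant Day 351 sample falls on Days 344–358, inside 323–378. Neither can reach 211–322. On the q8w schedule, those two trough days can therefore be filled only by unscheduled, ET or badly mistimed samples. A q6w participant can fill them: if q6w Day 1 were study Day 183, the next visits would be Day 225 (183 + 42), assigned to Day 239, and Day 267 (225 + 42), assigned to Day 295.

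**4. Effect on concentration.** Assume first-order decline with a half-life of 30–60 days; this range is an assumption. Ratio = 2^(days apart / half-life).

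| Comparison | 30 days | 40 days | 50 days | 60 days |
|---|---|---|---|---|
| 42 v 70 days (q8w extremes) | 1.91 | 1.62 | 1.47 | 1.38 |
| 47 v 65 days (Day 71 extremes) | 1.52 | 1.37 | 1.28 | 1.23 |
| 42 v 56 days (q6w v q8w, nominal) | 1.38 | 1.27 | 1.21 | 1.18 |

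**5. Typical rather than extreme spread.** If both visits fall independently and uniformly in their ±7-day windows, the simulated SD of the interval is 5.71 days. On the log scale s = (ln 2 / half-life) × 5.71, and the added geometric CV is √(exp(s²) − 1): 13.3%, 9.9%, 7.9% and 6.6% for half-lives of 30, 40, 50 and 60 days.

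**6. The predose time of 0.** Protocol 8.5.2 allows at most 0.5 h between a predose sample and the coming infusion. At a 30-day half-life that is 2^((0.5/24)/30) = 1.0005, a change of 0.05%. The recorded concentration itself does not change.

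**The case against.** Much of the case on the other side stands.

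A reader might infer that the predose time of 0 causes the pooling. It does not: it concerns the gap to the coming dose and alters no trough value. Nor does the SAP discard actual times, since it uses them after dosing and lists elapsed times and deviations in SAP 9.2.3. That listing helps less here than it might, because the same section treats predose samples as time 0 in each sampling period, so it need not show days since the previous infusion.

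The by-timepoint tables are not a breach, because Protocol 9.4.6 itself plans summaries at each sampling time. C_trough, C_max and the accumulation ratio take no elapsed time as a numerical input. SAP 9.3.1 does not say whether the slope uses nominal or actual day. Protocol 9.4 sends other changes in analysis methods to the clinical study report, so silence in SAP 14 is an omission rather than a breach.

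SAP 9.3.1 also equates troughs with predose concentrations, and SAP 6.4 picks the record nearest the middle of the window, so a scheduled sample normally wins where one exists. That defence fails on Days 239 and 295, where Table 2 schedules none. It is unclear on Day 351, where Table 2 marks no infusion for a sample to precede. It does not separate q6w or post-supplemental-dose samples, which are truly predose but follow a different interval.

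Finally, 42 to 70 days needs consecutive visits at opposite window limits.

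**Conclusion.** The point holds as a minor one. The trough and steady-state analysis lacks a criterion for time since the last infusion, this sits badly with the protocol's actual-time rule, and SAP 14 does not declare it. It is more than missing detail, because following the text can place q6w, ET or event-triggered samples in the steady-state contrasts, most clearly on Days 239 and 295.

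The in-window ranges come directly from the documents. The concentration effects rest on the assumed half-life and first-order decline, and the CV figures also on uniform visit timing. The extremes are sizeable and the typical effect is modest.

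A reader might go further and infer that the efficacy conclusions are at risk. The documents do not support that: SAP 8.1 classifies free C5-associated breakthrough hemolysis from measured free C5, not from the ravulizumab trough, and no primary or secondary efficacy endpoint uses this analysis.

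**What to change.** In SAP 9.2.2 and 9.3.1:

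- Derive actual time since the previous infusion for every PK sample.
- Count as C_trough only scheduled samples taken before an infusion, or the scheduled Day 351 sample, whose time since the last infusion lies within the range allowed by the two visits' protocol windows combined: 12–16 days for Day 15, 47–65 for Day 71, 42–70 for later q8w visits.
- Summarize or list q6w, post-supplemental-dose, ET and unscheduled samples separately.
- Use actual study day in the slope.
- Remove Days 239 and 295 from the q8w trough contrasts, or reconcile them with Protocol Table 2.
- Declare in SAP 14 any nominal-day rule that is kept.

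Two simpler remedies are best avoided. A ±7-day limit on the interval is not a protocol rule, since ±7 days applies to each visit. With whole-day uniform timing, 2 × (7 + 6 + 5 + 4 + 3 + 2 + 1) = 56 of 15 × 15 = 225 compliant visit pairs, about 25%, would be excluded. A time-since-dose covariate is largely confounded with visit, because Day 15 (12–16 days) does not overlap the later troughs (42–70 days).

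The cost is SAP wording and one derived variable from dose and sampling times already recorded. The downside is that a few samples leave the trough summary and appear in a listing. No new data and no change to treatment are needed.
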